Our plan is to conduct a randomized controlled trial of unblinded CGM among people with diabetes who are discharged home after being treated in the ED for diabetes-related emergencies. In conjunction with research assistants, ED clinicians at the University Campus, Memorial Campus, Marlborough Campus, Clinton Campus, and Leominster Campus will identify patients with diabetes (type 1 or 2) and hyper- or hypoglycemia who would benefit from follow up in the UMass Diabetes Center of Excellence (DCOE). The ED physician will place a referral, if necessary, and study staff will help arrange this follow up, scheduling an appointment within 2-3 weeks. In addition to this care coordination, half of the participants will receive a CGM placed by the patient or study staff in the ED, and all patients will receive written instructions about how to handle recurrent hyper- or hypoglycemia.

The primary outcomes will be the rate of attendance at the follow-up visit and be the change in diabetes-related quality of life as measured by the PAID-5 scale and the DDS. We hypothesize that having a CGM will decrease the no-show rate and increase clinic attendance and improved diabetes-related quality of life. Secondary outcomes will include hemoglobin A1c levels over time, ED utilization, emergency medical services utilization, hospitalizations, and major cardiovascular events within 6 months. Finally, we will assess provider satisfaction in the DCOE via a brief survey.

Focusing on a common but rarely studied clinical problem – the ED-to-clinic transition for people with diabetes – this project will promote inter-departmental collaboration between the ED and the DCOE and will directly improve care for people with diabetes, particularly those from disadvantaged groups. In addition to improving care coordination, we will rigorously assess the

usefulness of CGM in a novel context, generating preliminary data for future work and serving as an example for other medical systems regionally and around the world.

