9. STUDY TIMELINES*

Patient Subject Participant Involvement Timeline:

- ***Enrollment & Intake Visit: (Day 0)***
 - Informed consent
 - Non-biometric data – Contact information; Intake data points
 - Five-question Problem Areas in Diabetes (PAID-5) scale as well as the 17-question Diabetes Distress Scale (DDS) and supplemental questions will be administered
 - Device training (if randomized to CGM)

- Care coordination to DCOE (all patients)
- ***Outpatient Blood Sugar Monitoring (for intervention group only) (day 0-14)***
 - Continuous Glucose Monitoring – Sensor worn 24 hours a day for up to 14 days.
Data can be uploaded
- ***Follow Up: (~Day 14-21 post ED visit)***
 - Study team will meet patient at follow-up appointment
 - Biometric data – Downloaded
 - Non-biometric data – Five-question Problem Areas in Diabetes (PAID) scale as well as the 17-question Diabetes Distress Scale (DDS) and supplemental survey questions will be administered
 - Compensation (\$10)
- ***6 Months Follow up (no active patient involvement)***
 - Follow-up data points abstracted from electronic health record (EHR)

Provider Subject Participant Involvement Timeline:

- ***Follow Up: (~Day 14-21 post ED visit of patient subjects)***
 - Study team send survey questions to provider subjects immediately after they have a clinic encounter with a patient subject
 - This will be the only time point of participation for provider subjects

Study Timeline: We anticipate that recruitment will be complete by September 30, 2022. Primary data analysis will be complete by the end of March 2023.

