11. PROCEDURES INVOLVED*

Enrollment & Intake Visit of patient subjects:

- **Recruitment:** See Section 24. Research personnel will confirm subjects' pregnancy status by subject self report.
 - **Documents:**
 - **HIPAA Waiver**
 - **Info Sheet**
 - **Screening Log**
 - **Declined/Ineligible Log**
- **Consent:** See Sections 30 & 31
 - **Documents:**
 - **Consent**
 - **HIPAA Authorization**
- **Randomization:** Using the Redcap randomization module, patients will be randomized to the care coordination-only or care coordination plus CGM group
- **Master Code Contact Information:** Study Staff will obtain at least two ways (primary phone number and mailing address) to contact participants to schedule follow-up visits, completing a follow-up phone call if necessary, and to ensure the CGM equipment is returned.
 - **Documents:**
 - **Contact Info**
 - **Master Code**
- **Intake:** Study Staff will query EMRs to obtain the data points listed in the document below. Data collected will be verified with participants.
 - **Documents:**
 - **Intake Data- RA Facing**
 - **Intake Data- Patient Facing**
- **Device Training for intervention arm (CGM Arm only):** Half of the participants identified and enrolled as described above will be randomized to receive an unblinded CGM. We plan to use the 14-day Libre 2 CGM from Abbott. This device is a small disk (1.38 inches in diameter and 0.2 inches thick), and it weighs 0.18 ounces. After it is placed, a small (less than 0.4mm thick) sensor probe (not sharp) remains in the skin and can transmit continuous glucose data to a reader. The device can be submerged in water, and if it falls off, there will not be any significant bleeding. Study Staff will demonstrate the features and use of the CGM and sensor application (how the device should be worn, when it should be removed, the procedure to query the device for blood sugar readings using either a reader or smart phone application). After participants demonstrate an understanding of the use of the GCM, Study Staff will place the device on one of the participant's upper arms (patient choice) and monitoring will begin immediately after a

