60-minute calibration period. They will be instructed to wear the CGM for two weeks continuously (including during sleep and hygiene), although they will also be advised that they can remove the sensor at any time if it causes any discomfort or distress. Subjects will not be removed from the study if they chose to remove the CGM. Participants will receive an informational sheet that explains the basic functionality of the CGM and lists Study Staff contact information in the event that they have questions about the CGM or its readings.

→ **Documents:**

- **CGM Information for enrolled patients (CGM arm only)**

- **Mobile Reader (CGM Arm only):** Study Staff will set up the Libre dedicated reader for subjects. Study Staff will demonstrate the features and use of the device and provide participants with an informational sheet that explains how and when to use the reader. Currently, Abbott, the company that manufactures the Libre 2 CGM system, is developing a mobile phone-based app to replace the reader. This app is under FDA review but is not yet approved. If it is approved between now and the end of enrollment, we will give participants the choice of using either the designated reader or their phone, if they possess a compatible phone.

→ **Documents:**

- **CGM Information for enrolled patients (CGM arm only)**

- **Education on managing out of range blood sugars:** All patients will receive information on how to respond to out of range blood sugars and emergency contact information

→ **Documents:**

- **Information sheet: Hyperglycemia**
- **Information sheet: Hypoglycemia**

- **Initial questionnaires: Patients will be administered** the five-question Problem Areas in Diabetes (PAID) scale as well as the 17-question Diabetes Distress Scale (DDS), which produces a total score and four subscale scores (emotional burden, regimen distress, physician distress, and interpersonal distress). Finally, patients will be administered several supplemental questions pertaining to their perceptions of their healthcare and barriers to obtaining optimal glycemic control.

→ **Paper Log:** Study Staff will administer these questionnaires on tablets shared with patients

▪ **Documents:**

- » **Problem Areas in Diabetes (PAID-5) scale/Diabetes Distress Scale and supplemental questions**

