- **Diabetes Center of Excellence Care Coordination:** Study Staff will follow up with ED provider to ensure that patients' have clinically indicated referral to diabetes center of excellence

→ **Appointment scheduling:** RA will make an appointment for the patient before ED discharge, if possible. If this is not possible, RA will contact the patient after discharge to arrange a follow-up appointment.

Outpatient Blood Sugar Monitoring: The CGM will be worn on the participants' upper arm continuously for 14 days (or until it falls off or the patient decides to remove it)

[figure not shown]
Visit #1 (~Day 14-21 Post-Discharge of patient subjects)

- **Documents:**
 - **Visit Data (RA facing)**
 - **Problem Areas in Diabetes (PAID-5) scale/Diabetes Distress Scale and supplemental questions**
 - **Fact sheet for provider subjects**
 - **Provider satisfaction survey**
- **CGM Data:** Biosensor data will be downloaded and reviewed
- **Material Collection:** Study Staff will collect CGM readers
- **Compensation:** Participants will be offered \$10 worth of gift cards to a retail store for completing visit #1.
- **Provider Survey:** immediately following an encounter with a patient subject, the provider taking care of each patient will be contacted by the study team as potential provider subjects. Potential provider subjects subsequently will be sent an email solicitation to participate in a Redcap survey. A fact sheet will be provided with that email. The survey will consist of 4 questions pertaining to their satisfaction with patient subject care coordination and/or their CGM utilization. Providers may be sent multiple surveys if they see multiple subjects who are enrolled in the study. This is the only involvement of the provider subjects.
- **No Shows:** *RAs will reach out to subjects who miss their follow-up appointment to (1) help them reschedule and (2) ask that they fill out the post-intervention questionnaire via an online link (or mailed paper copy or via phone, if desired)*

Follow up Data Collection (~6 months Post-Discharge)

- **Documents:**
 - **6 month follow up datasheet**
- **Data Collection:** The study team will query the EHR to collect follow up data points about enrolled subjects

Figure 1: Procedural Flow Sheet

t

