24. LOCAL RECRUITMENT METHODS

Patient Subjects

Feasibility: As per Section 13, based on the number of patients presenting to the University ED with the qualifying chief complaint, the study team is confident that the appropriate number of subjects can be recruited during the study period.

Procedures: We have created a one-page basic *information sheet* to hand out to both potential and enrolled participants that outlines the study details in an easy-to-read format.

- Study staff will identify potentially eligible individuals through EHRs
- They will initially view:
 - (*ED-Based*) The individual's name, age, sex, presenting complaint, ED bed location, and treating physician's name from the ED tracking board
 - If the individual seems eligible based on the above information, Study Staff will query other portions of the EMR (medical history, current medications, past medications) to verify EMR-based eligibility.
 - If the individual still seems eligible, the data points initially viewed will be recorded on the *Screening Log*.
 - Study Staff will notify the potential participant's treating physician of eligibility, and ask if the treating physician plans to refer the patient to the DCOE
 - If the physician is not familiar with the DCOE, the study staff member will educate the physician as to the purpose and availability of the DCOE to help the physician determine if a referral is appropriate for the patient. The study staff will also be prepared to show physicians how to place a referral order
 - If the physician replies in the affirmative, the study staff will then request their permission to approach their patient and ensure that there are no additional barriers to enrollment from a clinical standpoint.
 - Potential participants will be approached by a member of the Study Staff regarding this research. Study Staff will ask for the individuals' permission to explain our study, give them time to read our *information sheet* and offer them the opportunity to participate.

Destruction of Identifiers:

- **Declined or Ineligible:** Identifiers from the *Screening Log* will be deleted within 24 hours and de-identified demographic information, along with any noted barriers to participation, will be transferred to *Declined/Ineligible Log*.

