Contact Info - Contact information will be collected using the Redcap (Contact	- *Identifiable information	- Authorized Study Staff	- N/A	- Contact information will be transferred to the Master Code following

Info) and then transferred to the Master Code				completion of the enrollment and intake visit and the Redcap form will be destroyed
Intake Data Collection Sheet – RA Facing Collected using the Redcap form *Also see Section 12	Study ID# only	Authorized Study Staff	Directly entered by the RA into Recap	1) Destroyed upon completion of data collection verification 2) REDCap database will be archived once results have been published
Intake Data Collection Sheet- Patient Facing Collected using the Redcap form *Also see Section 12	Study ID# only	Authorized Study Staff	Directly entered by the participant into a secure online database using survey mode (REDCap)	1) Destroyed upon completion of data collection verification 2) REDCap database will be archived once results have been published
Info Sheet- Hyperglycemia	- N/A	- N/A	- N/A	- N/A
Info Sheet- Hypoglycemia	- N/A	- N/A	- N/A	- N/A
Info Sheet- CGM	- N/A	- N/A	- N/A	- N/A
Baseline Problem Areas in Diabetes (PAID) scale/ Baseline Diabetes Distress Scale and supplemental questions - Direct entry into REDCap	- Study ID# only	- Authorized Study Staff & Support Personnel	- Directly entered by the participant into a secure online database using survey mode (REDCap)	- REDCap database will be archived once results have been published
2 Week Follow up Data Collection Sheet 1) Collected using the paper form 2) Entered into REDCap *Also see Section 12	1) Study ID# only 2) Same as above	1) Authorized Study Staff 2) Authorized Study Staff & Support Personnel	1) Securely stored in the PI's locked office 2) Secure online database (REDCap)	1) Destroyed upon completion of data collection verification 2) REDCap database will be archived once results have been published
2 Week Problem Areas in Diabetes (PAID) scale/Diabetes Distress Scale and supplemental questions	- Study ID# only	- Authorized Study Staff & Support Personnel	- Directly entered by the participant into a secure online database using survey mode (REDCap)	- REDCap database will be archived once results have been published

- Direct entry into REDCap				
Provider subject email solicitation	-N/A	- Authorized Study Staff & Support Personnel	-N/A	-N/A

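### Baseline PAID-5 and DDS are not fixed before randomization: Section 11 lists them after the arm is known, Section 9 lists them elsewhere, and the reviewed text states no order

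*Combined protocol and SAP*

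**What the plan says.** Section 11, under the enrollment and intake visit, lists recruitment and consent, and then randomization: "Using the Redcap randomization module, patients will be randomized to the care coordination-only or care coordination plus CGM group". Contact information, intake data, CGM training and placement, reader set-up and education on out-of-range glucose follow. Only then comes "Initial questionnaires: Patients will be administered", which introduces the PAID-5, the DDS and the supplemental questions.

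Section 9 uses a different order for Day 0. After consent and intake data it says that the PAID-5 and the "17-question Diabetes Distress Scale (DDS) and supplemental questions will be administered". The next item is "Device training (if randomized to CGM"). Randomization is not listed as a step, so its place relative to the questionnaires is left open.

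The data table in Section 26 names the form "Baseline Problem Areas in Diabetes (PAID) scale" but does not say whether baseline means before allocation. Section 13 says only that change runs from the ED visit to the follow-up appointment. The item captioned "Figure 1: Procedural Flow Sheet" in Section 11 was not reproduced in the text available for this review.

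Allocation is open: Section 4 says "half of the participants will receive a CGM placed by the patient or study staff in the ED", so participants can tell their arm once the device step is reached.

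**The concern.** A baseline is protected by randomization only if it is measured before the participant can react to the assignment. Here the outcome is self-reported distress, study staff administer the forms, and under Section 23 the research assistants both train participants on the CGM and give the questionnaires. Section 16 itself lists distress and raised awareness of blood sugar as possible effects of the device. Someone who has just been given a sensor, or has just learned that they will not get one, may answer differently from someone who does not yet know.

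The first DDS analysis in Section 13 is an unadjusted between-arm comparison of change from baseline. A difference between arms in baseline reporting would enter that comparison directly. The predictors named for the adjusted model (age, gender, time since diagnosis) would not correct it. The error could go either way: a raised CGM-arm baseline makes the device look better, and a lowered one hides a real benefit.

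**Working it through.** **Order of steps, side by side**

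| Step | Section 9 (Day 0) | Section 11 |
|---|---|---|
| Consent | first | before randomization |
| Randomization | not listed | directly after consent |
| Intake data | after consent | after randomization |
| Device training | after questionnaires | before questionnaires |
| PAID-5/DDS | before device training | after randomization, device placement, reader set-up and education |
| Care coordination | last | last |

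Section 11 is the only text that places randomization among the Day 0 steps, and it places it before the questionnaires. Section 9 is compatible with randomization on either side of them.

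**The plan's own DDS figure**

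Inputs from Section 13: SD 1.0 (applied there to the change), 100 per arm, detectable difference about 0.40. No alpha is given for the DDS; two-sided 0.05 is assumed.

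- SE of the difference in change = 1.0 × √(2/100) = 0.1414.
- Detectable difference at 80% power = (1.960 + 0.842) × 0.1414 = 0.396, which reproduces the stated figure.
- Power is 80.7% for a difference of 0.40 and 94.2% for 0.50.

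These figures assume a baseline unaffected by arm, so the fix changes none of them.

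**Effect of a baseline shift**

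Let d be the shift in the CGM arm's mean baseline caused by knowing the arm, with follow-up answers held fixed. The difference in change is then biased by d in absolute size. With no true effect, two-sided error = P(|Z + d/SE| > 1.96). The documents give no value for d, so a range is shown. The 80-per-arm column applies the 20% dropout from the attendance calculation to the DDS: 100 × 0.80 = 80, SE = √(2/80) = 0.1581.

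| d (assumed) | Error, 100 per arm | Error, 80 per arm | Power for a true 0.40 if the benefit is masked, 100 per arm |
|---|---|---|---|
| 0 | 5.0% | 5.0% | 80.7% |
| 0.05 | 6.4% | 6.2% | 69.7% |
| 0.10 | 10.9% | 9.7% | 56.4% |
| 0.20 | 29.3% | 24.4% | 29.3% |

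For d = 0.10 and 100 per arm: d/SE = 0.707; upper tail P(Z > 1.253) = 0.105; lower tail P(Z < −2.667) = 0.004; total 0.109.

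**When follow-up answers also shift**

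Let dB and dF be the reporting shifts in the CGM arm at baseline and follow-up. The change comparison is biased by dF − dB, and a follow-up-only comparison by dF. A simulation (10,000 runs, 80 per arm, score SD 1.0, assumed correlation 0.5 so that the SD of change is 1.0, no true effect) gave these mean differences:

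| dB | dF | Change | Follow-up only |
|---|---|---|---|
| 0.10 | 0 | −0.10 | 0.00 |
| 0.10 | 0.05 | −0.05 | 0.05 |
| 0.10 | 0.10 | 0.00 | 0.10 |
| 0 | 0.10 | 0.10 | 0.10 |

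A follow-up-only comparison is therefore free of dB but not of dF.

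**The case against.** The strongest reply is that the documents do not prove a post-allocation baseline. Figure 1 may give the order, and its absence from the reviewed text is not a gap in the plan. Section 9 is the list headed as a timeline, and it leans the benign way. Section 11 may be partly a list of topics: its referral check comes last, although Section 24 has staff "ask if the treating physician plans to refer the patient to the DCOE" before the patient is approached. All of this stands, and it is why the point is conditional. It does not remove the need for a change, because even if Figure 1 shows the benign order, Section 11 lists another.

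A second reply is that the harm is hypothetical and that reporting bias at follow-up remains in an open-label trial whatever the order. That is also correct. No passage gives a size for d, and the last table shows that equal shifts at both times cancel in the change score. But such cancellation is a matter of luck, and the plan should not rely on it.

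Third, REDCap handles both randomization and the questionnaires, and Section 13 keeps its audit trail active, so the actual order may be recoverable. That would help in describing what happened. It could not restore a baseline already taken with the arm known.

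**Conclusion.** The concern holds as a conditional one. Sections 9 and 11 place the questionnaires differently, no text in the reviewed documents puts them before randomization, and Section 11 followed as listed takes the baseline of a self-reported primary outcome after the arm is known. Any bias in the DDS comparison equals d when follow-up reports are unaffected. At an assumed d of 0.10, two-sided error is about 10.9% with 100 per arm or 9.7% with 80, assuming SD 1.0 for change and alpha 0.05. At d = 0 nothing is lost. The same reasoning applies to PAID-5, for which the plan gives no SD. The change should be made, with medium confidence that the problem is real in practice, given the unseen flow sheet.

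**What to change.** Check Figure 1 first. Then give one explicit order in Section 9, Section 11 and Figure 1: consent, intake data, PAID-5/DDS/supplemental questions, REDCap randomization, and after that device training and placement. Set REDCap so that the randomization step opens only once the baseline questionnaire record is saved. Saved need not mean complete, because Section 27 lets participants skip items.

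If patients have already been enrolled in Section 11's order, establish for each one the time of the questionnaire relative to randomization, from the REDCap audit trail where it shows this. Add a follow-up-only DDS comparison as a sensitivity analysis, and state that it removes only the baseline shift and not any effect of open allocation on follow-up answers.

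The cost is close to nil: a stated order within the same visit and one REDCap rule. The sensitivity analysis needs no new data, and the sample size does not change.

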6. INCLUSION AND EXCLUSION CRITERIA*

Patient Subjects:

Inclusion Criteria:

- Age 18 years or older
- Patients must be preparing for discharge from the emergency department after being treated for either hyperglycemia or hypoglycemia
- Patients must be either new referrals to the DCOE or existing DCOE patients in need of post-ED follow up
- Patients must have type 1 or type 2 diabetes
- Patients must be able to provide informed consent
- Patients must be fluent in English or Spanish

Exclusion Criteria:

- Current CGM use
- Need for hospital admission
- Upcoming computed tomography (CT) or magnetic resonance imaging (MRI) studies within 2 weeks, as these imaging modalities could potentially affect CGM performance
- Pregnant patients, as the device is not approved for pregnancy
- Any altered mental status, which would limit a patient's ability to consent to the study
- Patients who already have a longitudinal relationship with an outside endocrinologist
- Patients who have not been referred to the DCOE
- Prisoners
- Patients under age 18 years
- Patients who do not speak English or Spanish fluently

Justifications for Criteria:

-Our intervention targets patients with diabetes who are treated and discharged from the emergency department after being treated for either hyperglycemia or hypoglycemia.

-We will translate consent materials and patient instructions into Spanish. No additional languages are included as the CGM being used for the study and its associated reader only has English and Spanish menus and instructional manuals.

-Prisoners represent a special population that is routinely excluded from similar research studies. They represent an inaccessible population.

-Patients under eighteen are typically treated by pediatric endocrinologists and have different care regimens that are beyond the scope of this study.

-Pregnant women will not be included in this arm of the study as the CGM being utilized for this study is not FDA approved for use in pregnant women.

Provider Subjects:

Inclusion criteria for provider subjects will consist of licensed independent providers (NP, PA, MD, DO or MBBS) who provide subspecialty diabetes care to a patient subject enrolled in the study. Pregnant women may be included in this cohort as this study arm entails less than minimal risk and the study activities have no impact on pregnancy.

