Sample Size: The primary outcomes are the clinic attendance rate and the change in diabetes-related distress, as measured by the Diabetes Distress Scale (DDS) and PAID-5 scale between the ED visit and the follow-up appointment date (19). Secondary outcomes include repeat ED/EMS utilization over 6 months, repeat hospitalizations, major cardiovascular events, and changes in hemoglobin A1c. For clinic attendance, we will aim to achieve attendance at 80% of the scheduled clinic visits. For a one-sided test at alpha=0.025 of a single proportion against a standard proportion (0.80), we will have 80% power to detect a difference of 0.13 (0.80 – 0.67) with a sample size of 83 subjects in the CGM group. Adjusted for 20% dropout, we will need approximately 100 subjects/group. For the DDS outcome, we will compare the change from baseline to the end of follow-up in the DDS between the two groups. Although we will fit the trajectory of the DDS change in each group using all DDS measures in a mixed effects model with repeated measures (MMRM), for simplicity in sample size estimation, we will calculate the sample size for an unadjusted comparison of the change between the two treatment groups. Based on a study of 267 subjects with diabetes (19), the standard deviation of the DDS was 1.0 across the three sites in that study. The DDS is a questionnaire of 17 questions, each scored on a Likert scale of 1 (not a serious problem) to 6 (serious problem), with the overall score calculated as the mean score across the 17 items. Thus, the range of the overall score is 1.0 – 6.0. With 100 subjects in each group, we can detect a difference of about 0.40 in the DDS change between the two groups. The literature on the DDS does not identify a clinically meaningful difference although Fisher, Polonsky, Hessler, Mullan (2012) suggest a difference of 0.5 as meaningful (20). Thus, our sample size will achieve power of greater than 80% to detect that difference.

Analysis Strategy: As indicated in the Sample Size section above, for the clinic attendance rate, we will conduct the initial unadjusted analyses using an exact test of the frequencies under the presumed population proportion (0.80) and the observed proportion. Adjusted analyses will be conducted using a logistic regression model for the proportion of clinic visits attended as the outcome in the intervention group with predictors including age, gender, time since diagnosis of diabetes, and other factors of interest.

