Data for analysis will be downloaded directly from REDCap and converted to SAS datasets or R data frames for analysis. The downloaded datasets will be deidentified and are HIPPA as well as 21 CFR Part 11 compliant.

Provider Data:

We will present the data from the provider surveys in a descriptive fashion. For example, we will report the percentage of patients in the CGM arm whose provider found the data useful. We will also do subgroup analyses. Potential subgroups include the type of diabetes, whether or not the diabetes diagnosis is new, and whether or not the participant presented to the ED with hypo- or hyperglycemia.

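### Newly diagnosed patients may have a weakly informative Day 0 DDS/PAID-5, and the planned unadjusted change comparison makes no allowance for it, at a cost in precision and clarity

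*Combined protocol and SAP*

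**What the plan says.** **Who is enrolled.** Section 6 requires only that "Patients must have type 1 or type 2 diabetes" and that "Patients must be either new referrals to the DCOE or existing DCOE patients in need of post-ED follow up". Neither the inclusion nor the exclusion list sets a minimum time since diagnosis. Section 13 (Provider Data) names "whether or not the diabetes diagnosis is new" among its potential subgroups, so the plan expects such patients.

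**What is measured.** Section 9 places the first DDS and PAID-5 at "Enrollment & Intake Visit: (Day 0" and the second at about "Day 14-21 post ED visit". Section 11 (Initial questionnaires) describes the DDS as an instrument "which produces a total score and four subscale scores (emotional burden, regimen distress, physician distress, and interpersonal distress". Section 13 defines the primary distress outcome as the change "between the ED visit and the follow-up appointment date".

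**How it is analysed.** For the DDS, Section 13 states that "we will compare the change from baseline to the end of follow-up in the DDS between the two groups". The initial analysis is unadjusted. The adjusted analysis is an MMRM in which each DDS score enters as an outcome and time since diagnosis is one of the listed predictors. No interaction of that predictor with time is stated. Forest plots are planned for subgroups that are not named. No rule is given for scoring, or choosing a baseline for, a patient diagnosed at the index visit.

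**The concern.** Two of the four DDS subscales ask about a regimen and a physician. A patient told of the diagnosis hours earlier may have had neither in relation to diabetes. Two consequences are plausible: the Day 0 score may be less correlated with the follow-up score than in established patients, and the mean change may differ because the patient is meeting the disease for the first time.

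Either one widens the distribution of change scores when the two kinds of patient are pooled, which lowers power for a primary outcome. The reported mean change per arm also becomes an average over two groups whose change may mean different things. Because allocation is randomised, both arms are affected alike in expectation, so the treatment contrast is not systematically biased.

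**Working it through.** **Inputs from Section 13:** 100 per group; SD of the DDS 1.0; detectable difference about 0.40; a difference of 0.5 cited as meaningful. No alpha is stated for the DDS. I use two-sided 0.05, which matches the one-sided 0.025 given for attendance.

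**Step 1: reproduce the plan.** The standard error of the difference is 1.0 × √(2/100) = 0.1414.
- Detectable difference at 80% power: (1.960 + 0.842) × 0.1414 = 0.396, against the stated 0.40.
- Power at 0.40: Φ(0.40/0.1414 − 1.960) = 80.7%.
- Power at 0.5: Φ(0.50/0.1414 − 1.960) = 94.2%.

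The plan's 1.0 is the SD of the score, not of its change. The SD of change is √(2(1 − r)), which equals 1.0 only when the correlation r is 0.5.

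**Step 2: add newly diagnosed patients (assumed values).** Let p be their share, with r = 0 for them and 0.5 for the others, and let δ be the difference in mean change between the two groups, the same in both arms. Then

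variance of change = (1 − p) × 1 + p × 2 + p(1 − p)δ².

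| p | δ | SD of change | Detectable difference | Power at 0.40 | Power at 0.5 | Power at 0.5, 80 per arm |
|---|---|---|---|---|---|---|
| 10% | 0 | 1.049 | 0.416 | 76.9% | 92.1% | 85.4% |
| 10% | 1 | 1.091 | 0.432 | 73.7% | 90.0% | 82.6% |
| 20% | 0 | 1.095 | 0.434 | 73.3% | 89.8% | 82.3% |
| 20% | 1 | 1.166 | 0.462 | 67.9% | 85.8% | 77.4% |
| 30% | 0 | 1.140 | 0.452 | 69.9% | 87.3% | 79.2% |
| 30% | 1 | 1.229 | 0.487 | 63.4% | 82.0% | 73.0% |

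The last column applies the plan's 20% dropout, which Section 13 uses for attendance but not for the DDS.

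**Step 3: does the planned covariate help?** Write the MMRM mean as a + b·time + c·arm·time + g·(time since diagnosis). Subtracting Day 0 from follow-up leaves b + c·arm, and g cancels. A main effect moves both visits equally and does not adjust the change.

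**Step 4: what would help?** Model the follow-up score instead, with the same assumptions and an effect of 0.40.
- *Baseline, new-diagnosis indicator and their interaction.* The residual variance is 0.75(1 − p) + p, which is 0.775 at p = 10% and 0.825 at p = 30%. Power is 89.5% and 87.6%. Simulation at these settings gave 86-90%.
- *Baseline only, shift located in the Day 0 score.* The residual variance is 1 − [0.5(1 − p)]² / [1 + p(1 − p)δ²]. At p = 10%, δ = 0 it is 0.7975 (power 88.6%); at p = 30%, δ = 1 it is 0.899 (84.7%). The new-diagnosis terms therefore add about 1 to 3 points here.
- *Baseline only, shift located in the follow-up score.* The residual variance is 1 + p(1 − p)δ² − [0.5(1 − p)]². At p = 30%, δ = 1 it is 1.0875 (77.4%), so in that extreme case the terms add about 10 points.

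Most of the gain over the change score comes from baseline adjustment: in the worst row of the table, power rises from 63.4% to 84.7% or 77.4% before any new-diagnosis term is added.

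**Step 5: sensitivity to r.** If established patients had r = 0.7, with p = 20%, δ = 0.5 and r = 0 in the newly diagnosed, the variance is 0.8 × 0.6 + 0.2 × 2 + 0.16 × 0.25 = 0.92. The SD is 0.959 and the detectable difference is 0.38.

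For the PAID-5, Section 13 gives no SD or target difference, so no loss can be computed.

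**The case against.** The strongest reply is that the plan's power claim is tied to 0.5, and at 100 per arm that claim survives every row of the table. The 0.40 is what the sample happens to detect, not the difference that justifies it. This stands.

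A reader might infer that the stated 0.40 is not attained. The documents do not support that as a flat statement, because the share, the correlations and the shift are all assumed. Step 5 shows that a higher correlation in established patients brings the detectable difference below 0.40 even with 20% newly diagnosed. With a 10% share, a shift of 0.5 and no change in the SD within the newly diagnosed, power at 0.40 is 79.9% against 80.7%, which is trivial.

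A reader might also infer that a Day 0 score in these patients cannot reflect living with diabetes. The documents do not reproduce the items, some patients may have had symptoms or distress before diagnosis, and the primary DDS score is the mean of all 17 items rather than the two subscales. Nor is lacking a diabetes clinician peculiar to the newly diagnosed: Section 5 describes a target population without secure longitudinal care. Section 13 speaks of a new diagnosis, not of one made at the index visit. These points stand, so the claim is only that the score may carry less information.

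Finally, time since diagnosis, other unspecified covariates and subgroup plots are already planned. They help less than they seem to. The initial comparison is unadjusted, the main effect cancels (Step 3), and new diagnosis is named as a subgroup only for the provider data.

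**Conclusion.** The point holds as one of precision and interpretation. Newly diagnosed patients are eligible and expected, their Day 0 scores are the baseline for a primary change outcome, and neither the unadjusted comparison nor the stated MMRM adjusts the change for new diagnosis.

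Under the Step 2 assumptions, power for 0.40 at 100 per arm falls from about 81% to 63-77%, while power for 0.5 remains 82-92%. It drops below 80% only when 20% loss is added to the less favourable rows. The direction relies on the Day 0 score being less predictive, or the mean change different, in the newly diagnosed; the size relies on a share and correlations that the documents do not give. It would be wrong to read this as bias between arms or as evidence that the sample size is inadequate for the plan's own target.

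**What to change.** Keep all patients in the trial and in the attendance analysis, and specify the following before outcome data are examined.

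- Record at intake, or derive from time since diagnosis, whether diabetes was first diagnosed at the index ED visit (yes/no).
- For DDS and PAID-5, replace the unadjusted change comparison with a linear model of the follow-up score on arm, baseline score, new-diagnosis indicator and baseline × new-diagnosis. This retains the Day 0 score and lets the data set its weight. Discarding that score in the newly diagnosed is a poorer choice: it loses up to about 3 points of power if the score is informative.
- Add new-diagnosis × time to the MMRM.
- Report the result in previously diagnosed patients alone as a sensitivity analysis.

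The cost is SAP wording, two extra model terms and possibly one intake field; the intake sheets are not shown, so the field may already exist. Baseline adjustment supplies most of the benefit. The new-diagnosis terms add about 0-3 points when the shift lies in the Day 0 score, and more if it appears only at follow-up.
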